### 10.3.2 Imaging/Core Laboratory Endpoints

The imaging/core laboratory endpoints include the following:

1. Restenosis (≥50% restenosed of the stented segment of the target lesion) or Occlusion (100% occluded of the stented segment of the target lesion). The imaging assessments are adjudicated by DUS core laboratory or venography core laboratory where applicable;
2. Stent Fracture - assessed by x-ray core laboratory;
3. Delayed Stent Migration (position change of a venous stent observed with an imaging modality >1 cm from its original location at the conclusion of the index procedure, as determined with regard to a reference anatomic structure) - assessed by x-ray or Venography core lab

#### 10.3.2.1 Imaging Reporting Window

Imaging will be considered qualified by completion of the corresponding scheduled visit. For those subjects that missed the scheduled visit, the following reporting windows will be applied to qualify the unscheduled visit, if applicable. The study day used in following Table 4 for the window definitions is calculated as “assessment date” minus “Index procedure date”:

**Table 4. Imaging reporting window**

Study Visit	Target Day	Reporting Window
Index Procedure	Day 0	NA
30-Day	Day 30	NA
6-Month	Day 180	NA
12-Month	Day 360	Study Day 271 – 420

Study Visit	Target Day	Reporting Window
24-Month	Day 720	Study Day 421 – 780
36-Month	Day 1080	Study Day 781 – 1140

### 10.3.2.2 Primary Patency

#### **Primary Patency Composite Endpoint Determination**

Primary Patency has two components:

1. CD-TLR
2. Imaging endpoint of Occlusion/Restenosis

Primary patency endpoint determination will follow the rules described below:

1. Censor any imaging assessments or events after any TVR (not clinically driven) as this changes the vessel making the subject unevaluable for patency at 12 months. If the date of assessment > date of TVR, then set the value to 'missing'
2. All Subjects that had CD-TLRs within 390 days will be counted as Primary Patency Failure whether or not an imaging assessment is available after the CD-TLR event. Subjects with TVR (not clinically driven) before the CD-TLR will be censored.
3. The imaging component of the 12-month primary patency will be constructed based on 'AT' principle – prior events will not be carried over to a later visit. For each subject, qualified imaging assessment will be determined in the following order:
  - a. Venogram on scheduled 12-month visit regardless of window.
  - b. DUS on scheduled 12-month visit regardless of window
  - c. Venogram from unscheduled visit within the imaging window, choose the one closest to the target visit date if there are multiple
  - d. DUS on unscheduled visit within the imaging window, choose the one closest to the target visit date if there are multiple

Primary Patency at 24 months, and 36 months follow-up will be determined following the similar convention specified above for 12 months.

For each individual component of the primary patency endpoint, the rate will be calculated in the following way:

The proportion rate of CD-TLR will be constructed as a clinical/safety endpoint - number of subjects with CD-TLR over number of evaluable subjects through the cutoff of a reporting time point. For example, for 12-month CD-TLR under the primary patency endpoint, the cutoff to determine the numerator is 390 days – this includes any subjects who had their first CD-TLR within 390 days. The denominator will be all subjects that had CD-TLR or had no CD-TLR but had at least 330 days of clinical follow-up.

The CD-TLR Endpoint will be reported cumulatively.

The determination of imaging component of the occlusion/restenosis endpoint is described above.

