## 10.11 Unscheduled Visits

Unscheduled visits are additional non-scheduled visits that occur at times other than the predetermined intervals and during which an intervention in the target vein takes place. If the Abre stent(s) is(are) explanted, the subject will be followed for safety reporting only for 30 days post-explant. AE data should be collected on the AE eCRF, and study exit data should be collected on the Study Exit eCRF. It is not allowed to implant a new Abre stent during the reintervention. The following assessments will be completed and the data will be recorded on the Follow-up eCRF:

- Physical assessment of limbs
- Villalta Score and VCSS (for both limbs, should be taken before any intervention)
- Quality of Life Questionnaires: EQ-5D and VEINES-QOL/Sym (should be taken before any intervention)
- INR for subjects on warfarin
- Duplex ultrasound (target limb)
- Duplex ultrasound (contralateral limb); image of the CFV waveform only.
- Venogram (target limb)
- IVUS (target limb)
- Plain X-ray (target limb) is required pre and post re-intervention to assess for stent fracture

- Secondary procedure data
- Adverse events/device deficiency
- Medications: Antithrombotics, Antibiotics, Immunosuppressants, NSAIDs, Steroids, Diuretics, Calcium-channel blockers, Statins
- Discontinuation information (in case the subject ends involvement in the study)

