### **10.12.6.3 Intravascular ultrasound (IVUS)**

During the following timepoints, IVUS (target limb) is required:

- during the index procedure, IVUS was required, prior and post stent placement to aid with stent sizing and lesion assessment;
- during unscheduled follow-up visits, if the subject returns to the hospital at times other than the predetermined intervals and during which an intervention in the target vein takes place, prior and post intervention.

Furthermore, an IVUS (or venography) may have been performed during the screening for diagnostic purposes.

All IVUS examinations should be performed according to the core laboratory guidelines and are analyzed by an independent core laboratory (See **Section 13.4**).

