Further, as supportive analysis on the primary endpoints, time-to-event analysis for primary patency through 12 months will also be performed and serves as a secondary analysis. Kaplan-Meier (KM) estimates with 95% two-sided confidence interval using Peto formula will be reported for primary patency rate through 360 days as well as 390 days to accommodate the 12-month visit window. Subjects not experiencing the event by 12 months will be censored at 12 months or last known follow-up as defined in Appendix A, whichever is earlier. Subjects not experiencing the CD-TLR but experiencing the Target Vessel Revascularization (TVR) before 12-month imaging window will be censored at date of TVR when evaluating the 12-month primary effectiveness endpoint. The imaging assessment for such subjects that are available either on or before the TVR date, if within the 12-month reporting window, may still be used.

Sensitivity analyses for primary effectiveness endpoint include multiple imputation and tipping point analysis which are further explained in section 7.4.

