**Table 5. Primary Assisted Patency and Secondary Patency Endpoints**

Outcome Scenarios	Primary Patency	Primary Assisted Patency	Secondary Patency
Patent (DUS, Venogram) at 12 months, no CD-TLR and no TLR before 12 months	Success	Success	Success
Binary Restenosis/Occluded (DUS, Venogram) at 12 months, and no TLR (not clinically driven) before 12 months	Failure	Failure	Failure
TLR (not clinically driven) before 12 months, before any CD-TLR , before 12 month imaging	Missing	Missing	Missing
Patent Venogram, DUS) at 12 months, CD-TLR before 12 months due to restenosis but no occlusion	Failure	Success	Success
Patent (Venogram, DUS) at 12 months, CD-TLR before 12 months due to occlusion	Failure	Failure	Success
Image missing at 12 months, CD-TLR before 12 months due to restenosis but no occlusion	Failure	Missing	Missing
Image missing at 12 months, CD-TLR before 12 months due to occlusion	Failure	Failure	Missing

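### Images after a re-intervention are dropped by calendar date only, so the patency rules cannot tell a pre-treatment image from a post-treatment image of the same day

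*SAP*

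**What the plan says.** - **Principle (SAP 10.3.2.2, rule 1).** "Censor any imaging assessments or events after any TVR (not clinically driven) as this changes the vessel making the subject unevaluable for patency".
- **Working test (same rule).** "If the date of assessment > date of TVR, then set the value to" missing. Only a strictly later date removes an image.
- **SAP 7.9.1.2**, for subjects with a TVR but no clinically driven TLR (CD-TLR): imaging "available either on or before the TVR date, if within the 12-month reporting window, may still be used".
- **Rule 2.** "All Subjects that had CD-TLRs within 390 days will be counted as Primary Patency Failure whether or not an imaging assessment is available" afterwards.
- **Rule 3.** The order is scheduled 12-month venogram, scheduled DUS, unscheduled venogram, unscheduled DUS. Among several unscheduled images the analyst is to "choose the one closest to the target visit date if there are multiple". Table 4 sets that window at days 271 to 420, and SAP 10.3.2.1 opens it only to subjects who missed the scheduled visit. Primary patency at 24 and 36 months follows a similar convention.
- **Table 5.** Primary success needs no TLR before 12 months. All three patency measures are Missing for "TLR (not clinically driven) before 12 months, before any CD-TLR , before 12 month imaging".
- **Protocol 10.11** describes an unscheduled visit as one outside the planned intervals "and during which an intervention in the target vein takes place", with DUS, venogram, IVUS and X-ray. Imaging both before and after treatment is expressly required for X-ray (10.11) and for IVUS (10.12.6.3: "during which an intervention in the target vein takes place, prior and post intervention"). Protocol 10.12.6.1 requires a venogram at re-intervention without saying before or after.

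**The concern.** Rule 1 gives its reason: the re-intervention alters the vessel, so later images no longer describe the study stent. An image taken an hour after treatment has the same defect as one taken the next day, yet the date test keeps the first and drops the second. The diagnostic image that led to treatment, which is the valid one, carries the same date. Nothing in the SAP records whether an image was taken before or after treatment, and closeness to the target date cannot separate two images of one day.

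At stake is whether an affected subject counts as patent, failed or missing in the primary effectiveness analysis. As the text stands, that depends on which image is read. The same ambiguity carries forward to the later patency time points.

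**Working it through.** **Step 1: follow the rules through the cases they leave open.**

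*Case A: scheduled 12-month visit with same-day treatment.* DUS suggests at least 50% restenosis in a subject without symptoms, Protocol 10.9 calls for a venogram, and the lesion is treated that day. The dates are equal, so rule 1 keeps every image. Rule 3(a) takes the scheduled venogram but does not say which if there are two. The diagnostic run gives Failure; a post-treatment run gives Success. If the visit falls before 12 months (its window opens at day 330), Table 5 disagrees with both. Its success row is not met because a TLR preceded 12 months. Its row for TLR not clinically driven gives Missing if the post-treatment image is the one read. The pre-treatment image fits no row, because the restenosis row also requires no such TLR before 12 months.

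*Case B: scheduled visit missed, re-intervention not clinically driven on an unscheduled day in days 271 to 420.* Rules 3(c) and 3(d) apply. Two images of one date lie equally far from day 360, so closeness cannot choose. The earlier-assessment tie-break in SAP 10.3.3 is for clinic-visit endpoints and would not separate images of one date either.

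*Case C: CD-TLR before 12 months but inside the imaging window, with no scheduled 12-month image.* Primary patency is Failure under rule 2. Rule 1 does not reach this case, because it covers only TVR that is not clinically driven. Table 5 then gives:

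| Reason for CD-TLR | Same-day post-treatment image counted as patent (assisted / secondary) | That image not counted (assisted / secondary) |
|---|---|---|
| Restenosis, no occlusion | Success / Success | Missing / Missing |
| Occlusion | Failure / Success | Failure / Missing |

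**Step 2: reproduce the design.** Inputs from SAP 6.3: n = 160, performance goal 0.75, expected patency 0.857, pass if at least 131 are patent.

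- Alpha = P(X ≥ 131 | 160, 0.75) = 0.0247. The SAP prints 0.0247.
- Power = P(X ≥ 131 | 160, 0.857) = 0.9288. The SAP prints 0.9288.

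**Step 3: weight of one subject.** 1/160 = 0.625 point. At the pass line, with exact one-sided 97.5% lower limits:

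- 131/160 = 81.9%, limit 75.02%: pass.
- 130/160 = 81.25% (the subject is a failure), limit 74.33%: fail.
- 130/159 = 81.8% (the subject is missing), limit 74.87%: fail.

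**Step 4: effect on a false pass.** Let k be the number of true failures scored patent. The test then passes with 131 − k true successes, so the chance of passing at 75% true patency is P(X ≥ 131 − k | 160, 0.75). The documents do not give k; the range is an assumption.

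| k | 0 | 1 | 2 | 3 | 4 | 5 |
|---|---|---|---|---|---|---|
| Chance of passing | 0.0247 | 0.0384 | 0.0574 | 0.0831 | 0.1163 | 0.1575 |

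**The case against.** The strongest reply is that other rules already stop most of this.

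- Rule 2 fails every CD-TLR within 390 days, and the definition of clinically driven is broad (recurrent baseline symptoms or new target-limb symptoms).
- Table 5 denies primary success to anyone with a TLR before 12 months.
- SAP 10.3.2.1 keeps unscheduled images out unless the scheduled visit was missed, and a scheduled image taken before the re-intervention outranks an unscheduled one.
- Rule 1's first sentence already says that images after the TVR are unusable.
- Assisted and secondary patency are descriptive (SAP 7.9.3), and secondary patency by definition looks at the vessel after an intervention.

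Most of this stands and makes the exposure small. It does not close it. Table 5 and rule 1's first sentence conflict with the date test and with 7.9.1.2 rather than override them. Table 5's bar applies to a TLR before 12 months, while the window runs to day 420. Case A needs no missed visit.

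Four stronger readings are tempting, and the documents do not support them:

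- *Any stent found narrowed and re-opened can be scored patent.* Rule 2 excludes clinically driven cases within 390 days.
- *Every unscheduled image comes from a re-intervention day.* Protocol 10.12.6.1 also allows venograms at other times at the investigator's discretion.
- *A completion venogram is always among the images.* It is likely, but post-treatment imaging is expressly required only for IVUS and X-ray, and neither enters the patency order.
- *The error favours the device.* The same allowance keeps the pre-treatment image, which scores Failure. The direction depends on the image read.

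**Conclusion.** The gap in the text is certain: rule 1 and 7.9.1.2 keep every image of the re-intervention date, no pre/post distinction or same-date rule exists, and Table 5 gives a different answer when the re-intervention comes before 12 months. For primary patency it matters only for re-interventions that are not clinically driven, mainly Cases A and B, and only if a post-treatment venogram or DUS was taken.

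How many subjects this touches cannot be worked out from the documents. The literature figure of 8.3% TLR at 12 months would give 200 × 0.083 = 16.6 re-interventions of any kind. The documents do not give the share that is not clinically driven, falls on a qualifying image date and has a post-treatment image, so a reader should not infer that one or two subjects are affected. What can be said is the weight per subject: 0.6 point, and a false-pass chance of 0.0384 instead of 0.0247 for one true failure scored patent. These figures assume 160 evaluable subjects and the exact binomial method of the sample size calculation. Planned n, alpha and power are unchanged. The point merits correction because the rule contradicts its own reason, the result can turn on one subject at the pass line, and the convention extends to 24 and 36 months.

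**What to change.** 1. In SAP 10.3.2.2 rule 1 and SAP 7.9.1.2, state that on the date of any target-vein re-intervention only images acquired before the re-intervention starts, identified by a core-laboratory pre/post flag, may be used for primary patency at 12, 24 and 36 months. Replacing the strict inequality with greater-than-or-equal is not enough, because it would also discard the valid pre-treatment image.
2. In SAP 10.3.2.3, state that a same-day post-intervention image does not qualify as the time-point image for assisted or secondary patency.
3. Align Table 5 with both, including a row for a re-intervention that is not clinically driven with a qualifying pre-treatment image of the same date.
4. The protocol synopsis reports that the premarket application was submitted after the 12-month data were collected. For that analysis, check whether any image dated on a re-intervention day was used, and report how it was handled.

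The cost is a few sentences, one revised table and one flag on images that already go to the core laboratories, plus a check of the subjects with a re-intervention.

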## 10.10 24 and 36 Months ( $\pm$ 30 days) Post-Procedure Follow-Up Assessment

Subjects will be seen in the office at 24 months (690-750 days) and 36 months (1050-1110 days) post-procedure. The following evaluations will be completed and data recorded on the Follow-up eCRF:

- Physical assessment of limbs;
- Villalta Score and VCSS (both limbs);
- Quality of Life Questionnaires: EQ-5D and VEINES-QOL/Sym;
- INR for subjects on warfarin;
- Duplex Ultrasound (target limb);
- Duplex ultrasound (contralateral limb); image of the CFV waveform only.
- X-ray (target limb);
- Adverse events/device deficiency;
- Medications: Antithrombotics, Antibiotics, Immunosuppressants, NSAIDs, Steroids, Diuretics, Calcium-channel blockers, Statins;
- Discontinuation information (in case the subject ends involvement in the study).

In the event that an in-clinic 24 and/or 36 Month visit is unable to be performed (i.e. Missed Visit) a 'Phone Encounter' may be completed. The purpose of the 'Phone Encounter' is to capture subject status including the following:

- Date of contact (phone encounter)
- Medications: Antithrombotics, Antibiotics, Immunosuppressants, NSAIDs, Steroids, Diuretics, Calcium-channel blockers, Statins;
- Adverse events/device deficiency;

The 'Phone Encounter' does not replace the 24- and/or 36-month visit. If a 'Phone Encounter' is completed for the 36-month visit, the subject should not be immediately exited from the study. The site should continue to attempt to schedule an in-clinic visit as specified above when it is appropriate to do so and work with Medtronic to understand how long the study will remain open.

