### 7.9.1.2 Statistical Method

The primary patency rate is calculated as the number of subjects without loss of primary patency divided by the number of subjects having evaluable primary endpoint data for primary patency rate at 12 months.

Based on the literature (see ABRE CIP Appendix A Scientific Literature Search), the weighted mean expected primary patency was 85.7%. By subtracting a margin of indifference of 10% from expected performance ( $85.7\% - 10\% = 75.7\%$ ); consequently, the value of 75% is therefore taken as the performance goal for the current study. The 12-month patency rate and lower limit of the 97.5% one-sided confidence interval will be reported. The primary effectiveness objective will be met if the lower limit of the 97.5% one-sided confidence interval of the 12-month patency rate is above 75%.

For the primary effectiveness endpoint, subjects will be included in the analysis and considered evaluable if:

- (a) the subject experiences at least one clinically-driven target lesion revascularization within 390 days;
- or (b) the subject has occlusion or restenosis  $\geq 50\%$  of the stented segment of the target lesion confirmed by core laboratory at 12 months or
- (c) the subject has at least 330 days follow up without an event in the primary effectiveness endpoint.

For analysis of the imaging component of primary patency, if a subject has both a valid venogram and DUS during the 12-month follow-up period then the venogram will be used. If no venogram is available,

then the DUS will be used. This is an imaging endpoint. More details of the reporting rules are used to determine this endpoint can be found in section 10.3.2.

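### A clinically driven re-treatment after day 390, followed by a late but patent scheduled 12-month image, is scored as primary patency success

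*SAP*

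**What the plan says.** **CD-TLR component.** SAP 10.3.2.2, rule 2: "All Subjects that had CD-TLRs within 390 days will be counted as Primary Patency Failure whether or not an imaging assessment is available". SAP 7.1.3 and 7.9.1.2 use the same limit for evaluability ("the subject experiences at least one clinically-driven target lesion revascularization within 390 days"), and so does the component rate ("for 12-month CD-TLR under the primary patency endpoint, the cutoff to determine the numerator is 390 days").

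**Imaging component.** SAP 10.3.2.2, rule 3, ranks the images:
- 3a: scheduled-visit venogram, with no day limit.
- 3b: "DUS on scheduled 12-month visit regardless of window".
- 3c: unscheduled venogram inside the imaging window, nearest the target day.
- 3d: unscheduled DUS on the same terms.

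The window in SAP Table 4 is "Study Day 271 – 420". It applies only on the unscheduled route; SAP 10.3.2.1 says: "For those subjects that missed the scheduled visit, the following reporting windows will be applied to qualify the unscheduled visit". Rule 3 scores status at the visit and does not carry earlier findings forward.

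**Discarding later images.** Rule 1 begins "Censor any imaging assessments or events after any TVR (not clinically driven", and its bracket closes there. Its stated reason is that such a procedure alters the vessel. It does not mention clinically driven procedures.

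**Later visits.** Primary patency at 24 and 36 months is to be determined by a similar convention. No CD-TLR cut-off day is given for those visits under this endpoint.

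**The concern.** The two halves of the composite close on different days, and no rule covers a CD-TLR that falls after day 390 but before the image used for the 12-month visit. That image shows a stent which has already been re-opened for symptoms. It says nothing about whether the stent stayed patent unaided, yet it can score the subject as a success.

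This conflicts with the SAP's own reasoning. Rule 1 treats an image after a non-clinically-driven TVR as uninformative. A CD-TLR alters the vessel just as much, but the image after it is kept. On the same dates, the symptomatic failure receives the better score.

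Primary patency is the effectiveness endpoint tested against the 75% performance goal, so each subject's classification enters a pass/fail decision.

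**Working it through.** **1. The rules applied literally (SAP 10.3.2.2)**

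| Case | Score | Why |
|---|---|---|
| CD-TLR day 385; scheduled image day 410 patent | Failure | Rule 2 |
| CD-TLR day 395; scheduled image day 410 patent | **Success** | Rules 1 and 2 do not apply; 3a/3b take the scheduled image |
| CD-TLR day 395; scheduled image day 450 patent | **Success** | As above; no day limit |
| Non-clinically-driven TVR day 395; scheduled image day 410 patent | Missing | Rule 1 |
| Scheduled image day 380 occluded; CD-TLR day 395 | Failure | Scheduled image precedes the event |
| No scheduled visit; occluded pre-treatment venogram day 395; patent venogram day 415 | Failure | 395 − 360 = 35 days from target, against 415 − 360 = 55 |
| No scheduled visit; pre- and post-treatment venograms both day 395 | Undetermined | No tie rule for images |
| No scheduled visit; no usable re-intervention image; DUS day 415 patent | **Success** | 3d, inside the window |

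The solid case is the late scheduled visit. On the unscheduled route, protocol 10.11 and 10.12.6.1 require a venogram at any target-vein re-intervention. That venogram outranks DUS and, after day 390, lies nearer day 360 than any later venogram. The route is exposed only if the venogram is unusable or the post-treatment image is the one used.

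**2. Other text that might close the gap**
- Evaluability criterion (c), SAP 7.9.1.2, asks for at least 330 days of follow-up without an event. A subject re-treated on day 395 meets it. On the opposite reading the subject is dropped, not failed.
- The TVR censoring sentence in SAP 7.9.1.2 concerns subjects who have no CD-TLR.
- SAP Table 5 scores a patent image as primary patency failure if a CD-TLR came before 12 months. It does not define 12 months for this purpose; elsewhere the SAP uses 360 days (10.2) and 390 days (10.3.2.2).

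**3. Size at the pass line**

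Inputs from SAP 6.3: N = 160, null 0.75, expected 0.857, reject if at least 131 are patent.
- The plan's own figures reproduce: P(X ≥ 131 | 160, 0.75) = 0.0247 and P(X ≥ 131 | 160, 0.857) = 0.9288.
- One subject is 1/160 = 0.625 percentage points.
- Exact (Clopper-Pearson) one-sided 97.5% lower limits: 131/160, 75.02% (pass); 130/160, 74.33% (fail).
- If the one affected subject is set to missing instead of failure: 130/159, 74.87% (fail).

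So a recorded 131 containing one such subject fails under either treatment.

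**4. Assumed range for type I error**

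The documents give no frequency. Suppose a share m of true failures is scored as success when the true rate is 75%. The recorded rate is then 0.75 + 0.25m, and the chance of reaching 131 of 160 is:

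| m | Expected subjects (40 × m) | Type I error |
|---|---|---|
| 0 | 0 | 0.0247 |
| 1% | 0.4 | 0.0291 |
| 2.5% | 1 | 0.037 |
| 5% | 2 | 0.054 |

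This treats every affected subject as a true 12-month failure, which is the severe reading.

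**The case against.** **The endpoint is patency at 12 months, and the SAP closes CD-TLR at day 390 consistently.** The supportive Kaplan-Meier analysis also stops at days 360 and 390. A stent re-treated on day 395 may have been patent on day 390. This stands. A reader might infer that a recorded 131 with one or two such subjects is really 130 or 129, but the documents do not show that these subjects had failed by 12 months. They show that the image used is uninformative, which supports missing at least as well as failure.

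**The late window cuts both ways.** Occlusion first seen on a late scheduled image counts as failure even if it arose after day 390. This stands against any inference that the mismatch as a whole can only raise patency. The particular sequence described here can only favour success.

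**The case is rare.** The visit must fall outside the protocol's day 330–390 window, which is a deviation under protocol 10.13; no scheduled image may precede the CD-TLR; and the later image must be patent. At the planned 85.7% the expected count is 160 × 0.857 = 137. The chance of landing on 131 or 132, the counts that one or two reclassified failures could overturn, is 0.033 + 0.044, about 7.7%, before allowing for whether such a subject exists. This stands.

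**The later visits are descriptive.** This also stands: no performance goal applies at 24 or 36 months. After a 36-month phone contact, protocol 10.10 says: "The site should continue to attempt to schedule an in-clinic visit as specified above when it is appropriate to do so". Late scheduled images are therefore foreseeable there, but that instruction does not extend to 24 months and nothing says how late visits run.

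None of this supplies the missing rule.

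**Conclusion.** The gap is real and narrow. Read literally, SAP 10.3.2.2 scores Success for a subject with a CD-TLR after day 390 and a later patent image from a late scheduled 12-month visit, and that result contradicts the logic of rule 1. A reader might infer that the unscheduled route to day 420 is equally open. It is not, because the required re-intervention venogram normally gives failure there.

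The effect is probably small: 0.625 points per subject at N = 160, decisive only near the boundary. The boundary figures assume exactly 160 evaluable subjects. That is the planned minimum, and the analysis uses all available 12-month data, so the actual pass line may differ. The type I error range rests on assumed shares. The correction is worth making because the defect is certain and its cost low, not because the documents show that the 12-month conclusion was affected.

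**What to change.** Add to rules 1–3 of SAP 10.3.2.2:

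1. No image taken after any CD-TLR may be used to score primary patency as Success.
2. If the CD-TLR falls after the cut-off (day 390 at 12 months), use the last qualifying image before it. This includes the pre-treatment re-intervention venogram if it lies within the imaging window.
3. If there is no such image, set the imaging component to missing. Handle it through the planned multiple imputation and tipping-point analyses (SAP 7.4), and add a sensitivity analysis counting these subjects as failures.
4. State the matching CD-TLR cut-off days for 24 and 36 months and apply the same rule there.

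A broader rule, failing every subject whose CD-TLR precedes the image used, should not be adopted without an upper day. A CD-TLR on day 500 would then be a 12-month failure if the visit took place on day 510 but not if it took place on day 380, so failure would depend on how late the visit was.

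Protocol v2.0 reports that the 12-month data have already supported the premarket application. For that analysis, report the number of affected subjects and the patency rate under the corrected rule.

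The cost is a few sentences, one date check in the program and one sensitivity analysis. The patency rate or the evaluable number may fall slightly.
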